east	Eastern Association for the Surgery of Trauma Advancing Science, Fostering Relationships, and Building Careers
	EAST MULTICENTER STUDY DATA COLLECTION TOOL
Multicenter Study:	
Enrolling Center: Enrolling Co-investigator:	
Demographic Variables	
Age: Sex:	Weight (kg):
Description of Initial Injury	
Estimated time from injury to pro	esentation (in hours):
ISS: AIS Head/Neck	:: AIS Face: AIS Chest:
AIS Abdomen/Pelvis:	AIS Extremity: AIS External:
TRISS:	
Bicycle Pedest Assault Crush I Motorc Non-ac Sports Other/U	/ehicle Crash rian Struck t (by person or animal) njury ycle Crash/All-Terrain Vehicle (ATV) Crash ccidental Trauma (NAT)
Vital Signs on Presentation	
SBP: HR:	SpO2: GCS:
Admission Anticoagulation a	nd Reversal:
	tiplatelet therapy (defined as a patient home medication or present at time of

Admission Anticoagulation and Reversal (continued)
--

Anticoagulation/Antiplatelet agent (cheo Warfarin Apixaban Aspirin Ticagrelor	ck all tha	it are pr	esent at	time of i	initial trauma assessment): Rivaroxaban Dabigatran Clopidogrel Other
Reversal agents given (defined as a re- initial trauma assessment) (Circle one):		gent giv YES	en for ar	nticoagul NO	lation or antiplatelet therapy present durir
Reversal agent (check all that were given K centra Idarucizumab	en for re	versal o	of anticoa	agulatior 	n/antiplatelet therapy): Andexanet Vitamin K Other
Patient with coagulopathy present on a	dmissior	n? (Circ	le one):	YES	NO
Patient Initial INR:					
Initial Imaging/Injury Assessment					
Was an initial FAST performed? (Circle YES YES/positive	e one):	YES/r	negative		NO
Which area of the FAST was positive? Pericardial Right upper quadrant Left upper quadrant Suprapubic			apply):		
Was an initial CT scan performed? (Cir YES NO	cle one)		emergen	t OR	
Organs Injured (Circle one): LIVER SPLEEN		BOTH	I (Liver a	ind splee	en)
Grade of Liver (Circle one): 1	2	3	4	5	6
Grade of Spleen (Circle one): 1	2	3	4	5	
Repeat Imaging					
Was repeat imaging performed? (Circle	e one):	YES		NO	
If yes, CT or US? (Circle one):		СТ		US	
Time from initial presentation ir	hours:		_		
	ge (char Change	nge in p (instituti	onal rec	ommeno	dation, scheduled imaging)
Imaging Findings:					

Organ Specific Delayed Complications

Liver Complications (defined as complications found during hospital admission, check all that apply): Increased bleeding/increased hemoperitoneum Pseudoaneurysm
Hemobilia New area of hepatic injury not previously recognized on initial workup Hepatic infarct (not post intervention)
Abscess Fulminant liver failure
Bile leak/biloma
Unexpected thrombosis (of hepatic and related vessels) Need for OR/intervention other than initial Other:
Spleen Complications (defined as complications found during hospital admission, check all that apply): Increased bleeding/increased hemoperitoneum Pseudoaneurysm
Delayed rupture
New area of splenic injury not previously recognized on initial workup Splenic infarct (not post intervention) Abscess
Unexpected thrombosis (of splenic and related vessels)
Pancreatic fistula
Arteriovenous fistula Need for OR/intervention other than initial
Other:
Intervention Information
Initial Intervention (prior to repeat imaging, circle one): YES NO
Time from initial presentation in hours:
Type of intervention (check one): OR (damage control?) IR Other:
What was performed?
Post-Imaging Intervention (following repeat imaging, circle one): YES NO
Time from initial presentation in hours:
Type of intervention (check one):
OR
OR IR Other:
What was performed?

Intervention Information (continued)		
Was there a complication from an interv Migration of coil Rupture of vessel Pancreatic fistula post Abscess Need for repeat interv Other:	t-splenectomy rention/surgery	zation)? Check all that apply:
Transfusion Information Total refers t	o sum of product during admissio	n. Record in both units and volume (ml).
Transfusion during hospital admission?	(circle one): YES	NO
4h whole blood (units/ml):	4h pRBC (units/ml):	4h FFP (units/ml):
4h platelet (packs/ml):	24h whole blood (units/ml):	24h pRBC (units/ml):
24h FFP (units/ml):	24h platelet (packs/ml):	
Total whole blood (units/ml):	Total pRBC (units/ml):	
Total FFP (units/ml):	Total platelet (packs/ml):	_
VTE prophylaxis:		
Did patient receive VTE prophylaxis dur	ring admission? (Circle one):	YES NO
Timing of initiation of VTE propl	hylaxis from initial presentation in	hours:
Type of VTE prophylaxis (Chec Enoxaparin Subcutaneous Other:		
VTE documented? (Circle one):	YES NO	
Did the patient receive therapeutic antic	coagulation during their hospital ad	Imission? (Circle one): YES NO
Therapeutic Anticoagulation ag	ent:	
Outcome Data:		
Hospital LOS:		
ICU LOS:		
Mortality (Circle one): YES	NO	
Mortality timing from admission (in days	s):	

Outcome Data (continued):

Readmission within 30 days (Circle on	e):	YES		NO		
Readmission CT scan (Circle one):	YES		NO			
Readmission CT scan findings (organ	specific)	:				
Organ Specific Intervention Performed	on Read	dmission	(Circle	one):	YES	NO
Reason for Intervention on Readmission	on:					
Type of Intervention on Readmission:						

Eastern Association for the Surgery of Trauma

Advancing Science, Fostering Relationships, and Building Careers

EAST MULTICENTER STUDY DATA DICTIONARY

Radiographic Evaluation of Delayed Solid Organ Complications – Data Dictionary

Data Entry Points and appropriate definitions / clarifications:

Entry space	Definition / Instructions
Demographic Variables	
Age	Age of patient enrolled.
Sex	Sex of patient enrolled.
Weight	Weight of patient enrolled in kilograms.
Description of Initial Injury	
Estimated Time from Injury	Numerical value for time from injury to presentation at hospital (in hours). If unknown, 1 hour will be selected.
ISS	Numerical value for calculated ISS (ISS = Injury Severity Score)
AIS Head/Neck	Numerical Value for AIS body region = Head/Neck (AIS = Abbreviated Injury Score)
AIS Face	Numerical Value for AIS body region = Face (AIS = Abbreviated Injury Score)
AIS Chest	Numerical Value for AIS body region = Chest (AIS = Abbreviated Injury Score)
AIS Abdomen/Pelvis	Numerical Value for AIS body region = Abdomen/Pelvis (AIS = Abbreviated Injury Score)
AIS Extremity	Numerical Value for AIS body region = Extremity (AIS = Abbreviated Injury Score)
AIS External	Numerical Value for AIS body region = External (AIS = Abbreviated Injury Score)
TRISS	Numerical Value for calculated TRISS (TRISS = Trauma Injury Severity Score)

Description of Initial Injury (continued)

Mechanism of Injury	Single choice for best description of blunt mechanism (exclude penetrating mechanisms) Options include:
	Fall Motor Vehicle Crash Bicycle Pedestrian Struck Assault (by person or animal) Crush Injury Motorcycle Crash/All-Terrain Vehicle (ATV) Crash Non-accidental Trauma (NAT) Sports Injury Other/Unknown
Vital Signs on Presentation	
Initial SBP	Numerical Value for initial SBP (SBP = systolic blood pressure)
Initial HR	Numerical Value for initial HR (HR = heart rate)
Initial SpO2	Numerical Value for initial SpO2 (SpO2 = oxygen saturation)
Initial GCS	Numerical value for initial GCS score (GCS = Glasgow Coma Scale)
Admission Anticoagulation and Re	versal
Admission Anticoagulation/Antiplatelet	Yes/No dropdown menu. Yes = patient on anticoagulation and/or antiplatelet therapy at time of admission. No = no anticoagulation or antiplatelet therapy at time of admission.
Anticoagulation/Antiplatelet Agent	If yes checked for Admission Anticoagulation/Antiplatelet, description of anticoagulation/antiplatelet agent which was present on admission. Check all that apply:
	Warfarin Rivaroxaban Apixaban Dabigatran Aspirin Clopidogrel Ticagrelor Other
Reversal Agents Given	Yes/No dropdown menu. Yes = reversal for anticoagulation given. No = no reversal agents given.

Admission Anticoagulation and Reversal (continued)

Reversal Agent	If yes checked for Reversal Agents Given, description of reversal agents used. Check all that apply:
	K centra Andexanet Idarucizumab Vitamin K FFP Other
Patient History of Coagulopathy	Yes/No dropdown menu. Yes = Patient with history of coagulopathy on admission. No = Patient with no history of coagulopathy on admission.
Initial INR	Numerical value for patient's INR on admission. (INR = International Normalized Ratio)
Initial Imaging	
Initial FAST	Single choice for initial Focused Assessment with Sonography for Trauma (FAST). Options include:
	Yes: FAST performed on initial assessment, results not available.
	Yes/positive: FAST performed on initial assessment and positive defined by fluid present in at least one of four views.
	Yes/negative: FAST performed on initial assessment and negative defined by no fluid present in any of the four views.
	No: FAST not performed on initial assessment.
Area of FAST positive	If Yes/positive checked for Initial FAST, description of area of FAST which is positive. Check all that apply:
	Pericardial Right Upper Quadrant Left Upper Quadrant Suprapubic
Initial CT	Single choice for initial computed tomography (CT) scan of the abdomen/pelvis. Options include:
	Yes: CT scan performed on initial assessment.
	No: CT scan not performed on initial assessment.
	After emergent operating room (OR): CT scan performed after patient

Initial Imaging (continued).

Organs Injured	Single choice for organ injuries identified on initial CT scan or within OR if occurred before imaging. Options include:
	Liver: Hepatic injury of any grade present on initial CT scan or found in OR at initial emergent operation.
	Spleen: Splenic injury of any grade present on initial CT scan or found in OR at initial emergent operation.
	Both: Hepatic AND splenic injuries of any grade present on initial CT scan or found in OR at initial emergent operation.
Grade of Liver	Single choice for grade of hepatic injury following AAST grading scale. If no hepatic injury present, leave blank. Note: Advance one grade for multiple hepatic injuries up to grade 3. Options include:
	Grade 1: Subcapsular hematoma <10% surface area. Parenchymal laceration <1 cm in depth.
	Grade 2: Subcapsular hematoma 10-50% surface area; intraparenchymal hematoma <10 cm diameter. Laceration 1-3 cm depth and <10 cm length.
	Grade 3: Subcapsular hematoma >50% surface area; ruptured subcapsular or parenchymal hematoma. Intraparenchymal hematoma >10 cm. Laceration > 3 cm depth. Any injury in the presence of a liver vascular injury or active bleeding contained within liver parenchyma.
	Grade 4: Parenchymal disruption involving 25-75% of a hepatic lobe. Active bleeding extending beyond the liver parenchyma into the peritoneum.
	Grade 5: Parenchymal disruption >75% of hepatic lobe. Juxtahepatic venous injury to include retrohepatic vena cava and central major hepatic veins.
	Grade 6: Hepatic avulsion.
Grade of Spleen	Single choice for grade of splenic injury following AAST grading scale. If no splenic injury present, leave blank. Note: Advance one grade for multiple splenic injuries up to grade 3. Options include:
	Grade 1: Subcapsular hematoma <10% surface area. Parenchymal laceration <1 cm depth. Capsular tear.
	Grade 2: Subcapsular hematoma 10-50% surface area; intraparenchymal hematoma <5 cm. Parenchymal laceration 1-3 cm depth.
	Grade 3: Subcapsular hematoma >50% surface area; ruptured subcapsular or intraparenchymal hematoma ≥5 cm. Parenchymal laceration >3 cm depth.

	Grade 4: Any injury in the presence of a splenic vascular injury or active bleeding confined within the splenic capsule. Parenchymal laceration involving segmental or hilar vessels producing >25% devascularization.
	Grade 5: Any injury in the presence of splenic vascular injury with active bleeding extending beyond the spleen into the peritoneum.
Repeat Imaging	
First Repeat Imaging	Yes/No dropdown menu. Yes = Repeat abdominal imaging performed during same hospital admission. No = No additional abdominal imaging performed during same hospital admission.
First Repeat Imaging Type	If yes checked for First Repeat Imaging, single choice for type of repeat imaging. Options include: Computed Tomography (CT) Ultrasound (US)
First Repeat Imaging Hours from Admission	If yes checked for First Repeat Imaging, numerical value for when repeatimaging was performed in hours from admission.
Reason for First Repeat Imaging	If yes checked for First Repeat Imaging, single choice for best reason for scan. Options include:
	Clinical Change: Repeat imaging prompted by patient factors including, but not limited to, vital sign changes, lab abnormalities, abdominal pain, and patient symptoms.
	Non-Clinical Change: Repeat imaging prompted by institutional protocol/recommendations, individual physician practice pattern, or that performed on a scheduled basis.
First Repeat Imaging Findings	If yes checked for First Repeat Imaging, free text of organ specific (hepatic or splenic) imaging findings.
Organ Specific Delayed Complication	tions
Liver Complications	Liver specific complications found during hospital admission. Check all that apply. Options include:
	Increased bleeding, including increased hemoperitoneum. Pseudoaneurysm Hemobilia New area of hepatic injury not previously recognized on initial workup. Hepatic infarct (not post-IR/post-intervention). Abscess Fulminant liver failure Bile leak/biloma Unexpected thrombosis (of hepatic and related vessels) Need for OR/intervention other than initial Other (free text)

Organ Specific Delayed Complications (continued)

Spleen Complications	Spleen specific complications found during hospital admission. Check all that apply. Options include:
	Increased bleeding, including increased hemoperitoneum. Pseudoaneurysm Delayed rupture. New area of splenic injury not previously recognized on initial workup. Splenic infarct (not post-IR/post-intervention). Abscess Unexpected thrombosis (of splenic and related vessels) Pancreatic fistula Arteriovenous fistula Need for OR/intervention other than initial Other (free text)
Intervention Information	
Initial Intervention	Intervention for hepatic and/or splenic injury prior to repeat imaging (can occur post-initial imaging assessment). Yes/No dropdown menu. Yes = intervention performed for hepatic and/or splenic injury at initial assessment, prior to repeat imaging. No = no intervention performed for hepatic and/or splenic injury at initial assessment, prior to repeat imaging.
Initial Intervention Timing	If yes checked for Initial Intervention, numerical value for time to intervention from presentation (in hours).
Initial Intervention Type	If yes checked for Initial Intervention, single best choice for type of intervention performed. Options include:
	OR: Patient taken to operating room.
	Damage Control: Operation specifically described as damage control or patient described as unstable.
	Planned OR: Operation on stable patient.
	Interventional Radiology (IR): Patient taken to IR suite for intervention.
	Other
Initial Intervention Description	If yes checked for Initial Intervention, free text briefly describing organ specific (hepatic or splenic) intervention.
Post-Imaging Intervention	Intervention for hepatic and/or splenic injury following repeat imaging (as a result of the imaging findings). Yes/No dropdown menu. Yes = intervention performed for hepatic and/or splenic injury following repeat imaging. No = no intervention performed for hepatic and/or splenic injury following repeat imaging.
Post-Imaging Intervention Timing	If yes checked for Post-Imaging Intervention, numerical value for time to intervention from presentation (in hours).

Intervention Information (continued)

	_
Post-Imaging Intervention Type	If yes checked for Post-Imaging Intervention, single best choice for type of intervention performed. Options include:
	OR: Patient taken to operating room.
	Interventional Radiology (IR): Patient taken to IR suite for intervention.
	Other
Post-Imaging Intervention Description	If yes checked for Post-Imaging Intervention, free text briefly describing organ specific (hepatic or splenic) intervention.
Intervention Complication	Complications of organ specific (hepatic or splenic) interventions which occurred during the hospitalization. Check all that apply. Leave blank if no complications of interventions found.
	Migration of coil Rupture of vessel Pancreatic fistula post-splenectomy Abscess
	Need for repeat intervention/surgery Other (free text)
Transfusion Information	
Transfusions	Yes/No dropdown menu for transfusions during hospital admission. Yes = patient received blood products (whole blood, pRBCs, FFP, platelets) during hospital admission. No = patient did not receive blood products during hospital admission.
4h Whole Blood Total Units	Total units of Whole Blood administered in the first 4 hours (4h) from presentation.
4h pRBC Total Units	Total units of Packed Red Blood Cells (pRBC) administered in the first 4 hours (4h) from presentation.
4h FFP Total Units	Total units of Fresh Frozen Plasma (FFP) administered in the first 4 hours (4h) from presentation.
4h Platelet Total Packs	Total packs of Platelets administered in the first 4 hours (4h) from presentation.
24h Whole Blood Total Units	Total units of Whole Blood administered in the first 24 hours (24h) from presentation.
24h pRBC Total Units	Total units of Packed Red Blood Cells (pRBC) administered in the first 24 hours (24h) from presentation.
24h FFP Total Units	Total units of Fresh Frozen Plasma (FFP) administered in the first 24 hours (24h) from presentation.
24h Platelet Total Packs	Total packs of Platelets administered in the first 24 hours (24h) from presentation.

Transfusion Information (continued)

Total Whole Blood Units	Total units of Whole Blood administered during hospital admission.
Total pRBC Units	Total units Packed Red Blood Cells (pRBC) administered during hospital admission.
Total FFP Units	Total units Fresh Frozen Plasma (FFP) administered during hospital admission.
Total Platelet Packs	Total packs of Platelets administered during hospital admission.
4h Whole Blood Total Volume	Total volume in ml of Whole Blood administered in the first 4 hours (4h) from presentation.
4h pRBC Total Volume	Total volume in ml of Packed Red Blood Cells (pRBC) administered in the first 4 hours (4h) from presentation.
4h FFP Total Volume	Total volume in ml of Fresh Frozen Plasma (FFP) administered in the first 4 hours (4h) from presentation.
4h Platelet Total Volume	Total volume in ml of Platelets administered in the first 4 hours (4h) from presentation.
24h Whole Blood Total Volume	Total volume in ml of Whole Blood administered in the first 24 hours (24h) from presentation.
24h pRBC Total Volume	Total volume in ml of Packed Red Blood Cells (pRBC) administered in the first 24 hours (24h) from presentation.
24h FFP Total Volume	Total volume in ml of Fresh Frozen Plasma (FFP) administered in the first 24 hours (24h) from presentation.
24h Platelet Total Volume	Total volume in ml of Platelets administered in the first 24 hours (24h) from presentation.
Total Whole Blood Volume	Total volume in ml of Whole Blood administered during hospital admission.
Total pRBC Volume	Total volume in mI Packed Red Blood Cells (pRBC) administered during hospital admission.
Total FFP Volume	Total volume in ml Fresh Frozen Plasma (FFP) administered during hospital admission.
Total Platelet Volume	Total volume in ml of Platelets administered during hospital admission.

Prophylactic and Therapeutic Anticoagulation

VTE Prophylaxis

Yes/No dropdown menu for if patient received venous thromboembolism (VTE) prophylaxis during hospital admission. Yes = patient received VTE prophylaxis during hospital admission. No = patient did not receive VTE prophylaxis during hospital admission.

Prophylactic and Therapeutic Anticoagulation (continued)

Timing of VTE Prophylaxis	If yes checked for VTE prophylaxis, numerical value for timing of initiation of VTE prophylaxis from admission (in hours).
Type of VTE Prophylaxis	If yes checked for VTE prophylaxis, single best choice for agent used for VTE prophylaxis. Options include:
	Enoxaparin Subcutaneous Heparin (SQH) Other
VTE Documented	Yes/No dropdown menu for if VTE was documented during hospital admission. Yes = VTE documented during hospital admission. No = VTE not documented during hospital admission.
VTE Type	If yes checked for VTE documented, single best choice for type of VTE. Options include:
	Pulmonary embolism (PE) Deep Vein Thrombus (DVT) Other
Therapeutic Anticoagulation	Yes/No dropdown menu for if the patient received therapeutic anticoagulation during hospital admission. Yes = patient received therapeutic anticoagulation during hospital admission. No = patient did not receive therapeutic anticoagulation during hospital admission.
Therapeutic Anticoagulation Agent	If yes checked for Therapeutic Anticoagulation, free text to best describe anticoagulation agent used (i.e. Warfarin, Therapeutic Enoxaparin, Heparin drip, etc.).
Outcome Data	
Hospital LOS	Free text entry for number of consecutive days the patient was hospitalized at initial admission (in days). Day of admission = hospital day 1. (LOS = length of stay)
ICU LOS	Free text entry for number of consecutive days the patient required ICU admission (in days). ICU = Intensive Care Unit. Day of admission = hospital day 1. (LOS = length of stay)
Mortality	Yes/No dropdown menu for patient mortality. Yes = patient expired during initial hospitalization. No = patient did not expire during initial hospitalization.
Mortality Timing from Admission	If yes checked for Mortality, free text numerical value for time of death from admission (in days). Day of admission = hospital day 1.

Outcome Data (continued)

Readmission within 30 days	Yes/No dropdown menu for readmission within 30 days of hospital discharge. Readmission specifically for splenic or hepatic injury (not for concomitant injuries). Yes = patient readmitted within 30 days of initial discharge. No = patient not readmitted within 30 days of initial discharge.
Readmission CT scan	Yes/No dropdown menu for readmission CT scan. Yes = CT scan performed during readmission. No = No scan performed during readmission. If multiple scans were performed, select Yes.
Readmission CT scan findings	Free text entry for organ specific (splenic or hepatic) findings on readmission CT scan.
Intervention Performed on Readmission	Yes/No dropdown menu for intervention performed on readmission. Only include interventions performed for splenic or hepatic injury. Yes = intervention performed for splenic or hepatic injury on readmission. No = no intervention performed on readmission for splenic or hepatic injury.
Reason for Intervention on Readmission	Free text entry for reason for organ specific intervention upon readmission.
Type of Intervention on Readmission	Free text entry for type of intervention performed on readmission.

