The time frame for data query will be from IRB approval (2020) until December 31, 2023. The electronic medical record (EMR) may be used in order to identify participants who match study defined demographic criteria.

Primary Outcome: Delayed complications found on repeat imaging

Secondary Outcomes: Timing to repeat imaging/ intervention, interventions performed based on complications found, mortality, length of stay, blood transfusion requirements, VTE prophylaxis, and 30 day readmission variables [readmission within 30 days for spleen and/or liver injury, readmission CT scan, interventions performed].

Variables

List specific variables to be collected & analyzed: Age, sex, time from injury, Injury Severity Score (ISS), Abbreviated Injury Scale (AIS), Trauma and Injury Severity Score (TRISS), mechanism of injury, initial vital signs, anticoagulant use and reversal agents, initial and repeat imaging, grade of organs injured, complications found, details regarding initial and any delayed interventions, blood transfusions, details regarding venous thromboembolism prophylaxis, venous thromboembolism complications, hospital length of stay, intensive care unit length of stay, mortality, and 30 day readmission variables [readmission within 30 days for spleen and/or liver injury, readmission CT scan, interventions performed].

Data Collection and Statistical Analysis

Standardized data will be collected for each patient meeting inclusion criteria (see data collection tool). The de-identified data for each patient will be entered into a secure REDCap database. A total of 5,000 patients (3,500 splenic injuries and 1,500

hepatic injuries) is recommended to identify a significant difference between the non clinical change and clinical change group. Complications found on repeat imaging will be assessed using univariate and multivariate analysis.

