Categorical variables will be compared using Fisher's exact test or Chi-squared test. Continuous variables will be assessed using Student's t-test. For multivariate analysis, a mixed effect multinomial logistic regression will be run with a binary outcome of whether the patient had a delayed complication. Another mixed effect multinomial logistic regression will be run with a binary outcome of whether the patient had an intervention performed. Additional analysis will be completed to determine if there is optimal timing for repeat imaging to identify complications. Data will be reported as adjusted odds ratios with 95% confidence intervals. Statistical significance will be defined by a p<0.05.

Sample Size and Power Estimates

A retrospective pilot study was completed with 235 patients with splenic injuries and 365 hepatic injuries. Of the patients with splenic injuries, 105 underwent repeat imaging, 46 had organ specific complications, and 16 had an intervention performed. Of the patients with hepatic injuries, 122 underwent repeat imaging, 30 had organ specific complications, and 12 had an intervention performed.

Spleen Power Analysis

Combined complication rate for patients who had repeat imaging: 46/105 = 0.44Standard protocol complication rate: 18/38 = 0.47Physician discretion complication rate: 28/67 = 0.42

Complication Rate:	Complication Rate:	Odds Ratio	Sample Size
Standard protocol	Physician discretion		(Total Population)
0.46	0.43	0.89	8,614
0.47	0.42	0.82	3,100
0.48	0.41	0.75	1,582

Liver Power Analysis

Combined complication rate for patients who had repeat imaging: 30/122 = 0.25Standard protocol complication rate: 10/50 = 0.20Physician discretion complication rate: 20/72 = 0.27

Complication Rate: Standard protocol	Complication Rate: Physician discretion	Odds Ratio	Sample Size (Total Population)
0.21	0.26	1.32	2,256
0.20	0.27	1.48	1,150
0.19	0.28	1.66	696

Consent Procedures

This is a retrospective observational study in which data will be retrospectively recorded on patients according to institutional protocols. Data will be input into REDcap database without any patient identifiers. Thus, a waiver of consent is requested.

Confidentiality and Privacy

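### Unknown injury-to-presentation times are stored as 1 hour with no flag, and the form and dictionary time repeat imaging and VTE prophylaxis from different origins

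*Supplement*

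**What the plan says.** The Data Dictionary entry for Estimated Time from Injury, under Description of Initial Injury, asks for a number of hours from injury to hospital presentation and adds: "If unknown, 1 hour will be selected". The Data Collection Tool gives this item one blank for hours.

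The protocol's Variables section includes the item among those to be used: "List specific variables to be collected & analyzed: Age, sex, time from injury". The Data Collection and Statistical Analysis section plans a timing analysis without naming its clock: "Additional analysis will be completed to determine if there is optimal timing for repeat imaging to identify complications". It lists no covariates for the regression models and no method for missing data.

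On time origins, the tool's Repeat Imaging block asks for "Time from initial presentation" in hours, and its VTE prophylaxis block also counts from initial presentation. The dictionary counts both from admission. Initial and post-imaging interventions are counted from presentation in both documents.

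**The concern.** A missing-value code should be a value that cannot occur. One hour is a common, plausible time to presentation, so the rule turns missing data into apparently valid data. Elsewhere the dictionary keeps the two apart. Initial FAST has its own category ("Yes: FAST performed on initial assessment, results not available"), mechanism has an Other/Unknown option, and the grade of an uninjured organ is left blank.

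Time from injury matters in three places: as a description of the cohort, as a possible covariate in the models for delayed complication and for intervention, and in any attempt under Aim 2 to express the best imaging time as time since injury. Imaging is clocked from presentation or admission, so time since injury can only be obtained by adding this field. If unknown times belong mainly to patients who arrived late, the stored value is too short for exactly the patients furthest from injury.

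The mixed time origin is a separate fault. Timing to repeat imaging and intervention is a named secondary outcome. One site may follow the form and another the dictionary, and imaging and intervention times may then start from different points.

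**Working it through.** The plan gives no figure for this point, so there is none to reproduce. The masking follows from the rule alone. The rest is illustration, and every input in steps 1 to 3 is an assumption.

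**1. How mixed the 1-hour records become.** Let u be the share of unknown times and p the share of known times that round to 1 hour. The share of 1-hour records that are really unknown is u / (u + (1 − u)p). Assume 90% of patients present early (lognormal, median 1.2 h, log-SD 0.6) and 10% late (median 24 h, same log-SD). Counting known times below 1.5 h as 1 hour, p = 0.90 × Φ(ln(1.5/1.2)/0.6) = 0.90 × 0.645 = 0.58; late presenters add almost nothing.
- u = 5%: 0.05 / (0.05 + 0.95 × 0.58) = 0.05 / 0.601 = 8%.
- u = 20%: 0.20 / (0.20 + 0.80 × 0.58) = 0.20 / 0.664 = 30%.

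**2. Effect on a per-hour odds ratio.** Let known times have mean μk and variance σ², unknown times have mean μu, and the effect be linear with slope β. With unknowns set to 1, the fitted slope is approximately

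β × [σ² + u(μk − 1)(μk − μu)] / [σ² + u(μk − 1)²].

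Take exponential known times with μk = 2 h, so σ² = 4, and a true odds ratio of 1.05 per hour, so β = ln 1.05 = 0.0488.

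| Mean of unknown times | u = 10% | u = 20% | u = 30% |
|---|---|---|---|
| 2 h (same as known) | 4.0/4.1 = 0.976, OR 1.049 | 4.0/4.2 = 0.952, OR 1.048 | 4.0/4.3 = 0.930, OR 1.046 |
| 6 h | 3.6/4.1 = 0.878, OR 1.044 | 3.2/4.2 = 0.762, OR 1.038 | 2.8/4.3 = 0.651, OR 1.032 |
| 12 h | 3.0/4.1 = 0.732, OR 1.036 | 2.0/4.2 = 0.476, OR 1.024 | 1.0/4.3 = 0.233, OR 1.011 |

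Logistic simulations on these inputs agree closely, with slightly more attenuation in the 12 h row (down to about 1.006). Leaving the unknowns out returns about 1.05.

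The second term of the numerator comes from the difference in risk between known and unknown patients. Here that difference arises only through time. If unknown patients have lower risk for some other reason, the term turns positive and the slope can be overstated. The direction is therefore not fixed by the rule.

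**3. Effect on a late-versus-early contrast.** Use the step 1 times with assumed complication risks of 45% at 6 h or more and 30% below. The true odds ratio is (0.45/0.55)/(0.30/0.70) = 1.91. The share truly at 6 h or more is 0.102. If 40% of these are stored as 1 hour, they make up 0.0409 / (0.898 + 0.0409) = 4.4% of the recorded early group. Its risk becomes 0.30 + 0.15 × 0.044 = 0.3065, and the odds ratio becomes 0.818/0.442 = 1.85. With only 5% stored as 1 hour it is 1.90.

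**4. Time origin.** Assume 2 to 6 h between presentation and admission. The pilot's mean times to identifying complications were 2.4 and 4.4 days, or 57.6 and 105.6 h. The shift is then between 2/105.6 = 2% and 6/57.6 = 10% of those times.

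**The case against.** **The field is peripheral.** The primary outcome and the comparison of clinical-change with non-clinical-change imaging do not use time from injury. No model is said to include it, and Aim 2 can be analysed on the recorded presentation or admission clock. This stands. A reader might infer that the primary result, or the optimal imaging time, is compromised; the documents do not support that.

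**The bias is assumed.** This also stands. Nothing in the documents says that unknown times cluster in late presenters or gives their frequency. If they resemble known times, the attenuation is small (first row of the table). A reader might infer a certain bias toward the null; only the masking is certain.

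**It can be repaired later.** Every unknown sits at exactly 1, so an analyst could set all 1-hour records to missing, and a simulation of that step returned odds ratios of 1.046 to 1.050 against a true 1.05. Records are also kept for 6 years, so sites could go back to the charts. A reader who infers that the damage is beyond repair therefore goes too far. But the repair is partial: on the step 1 inputs it discards 60% to 66% of all records, including every genuine 1-hour case, and no chart re-check is planned.

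**The clock conflict is only wording.** It is hours against days, and an imaging-to-intervention interval is not a specified outcome. That limits its weight, but the two documents still give sites different instructions for a named secondary outcome.

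**Conclusion.** The point holds, with limited reach. Following the dictionary as written puts false values into a listed analysis variable and removes the means of identifying them within the data set. Any time-from-injury description, covariate or time-since-injury analysis can be biased. On the assumed inputs the effect ranges from negligible (1.05 to about 1.046–1.049 per hour) to near removal of the association (about 1.01), and the late-versus-early odds ratio moves from 1.91 to 1.85 when 40% of late times are masked. Which of these applies depends on the share and type of patients with unknown times, which the documents do not give.

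The time-origin conflict between form and dictionary is real and independent of this, and probably small. Both should be fixed. Neither is shown to undermine a primary or fully specified analysis, so a higher grade is not supported.

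**What to change.** - Delete the 1-hour rule. Leave the field blank when the time is unknown and add an injury-time-unknown tick box to the form, the dictionary and REDCap.
- Ask sites to check existing entries of exactly 1 hour against the chart and flag those that were unknown. Do this while the charts and study identifiers can still be linked.
- State in the analysis section that unknown times are missing: complete-case analysis with multiple imputation as a sensitivity analysis, or the reverse. Report both, because standard imputation may itself be biased if being unknown depends on the true time. Report the number unknown.
- Give repeat imaging and VTE prophylaxis the same origin in form and dictionary, namely the presentation origin already used for interventions. Confirm which origin sites have used so far.

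The cost is one tick box, a few dictionary lines and a small site query. The only downside is that the missing data become visible.
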